### **Statistical Approach & Expected Outcomes**

**General Data Analytic Approach.** We will conduct repeated measures analyses (i.e., across time) using generalized linear mixed modeling (GLMM; Proc MIXED, Proc GLIMMIX, and Proc MCMC; SAS 9.4). Continuous and count data will be analyzed using linear and Poisson regression, respectively (Proc GENMOD; SAS v. 9.4). Evaluation of distributional assumptions will use residual plots and, where possible, formal statistical tests. Depending upon statistical technique, we will address violations of assumptions using transformations, robust estimators, stratification, and/or scaling coefficients. For instance, given the characteristically skewed nature of the TNE distribution the analytic plan and power discuss this variable in its log form. Analyses of data with missing values will utilize multiple imputation for cross-sectional analyses (Proc MI and Proc MIANALYZE; SAS v.9.4) [126], while analyses of repeated measures will rely on GLMM to maximize use of existing data. For analyses that require assessment for differential patterns of missing data, we will use Little's Test of MCAR for continuous outcomes and the Park and Lee's approach for discrete outcomes [127, 128]. We will use pattern-mixture modeling methods to address non-ignorable missing data patterns [129]. We will use sensitivity analyses to evaluate the robustness of findings to missing data assumptions. Finally, the False Discovery Rate approach will be used to correct for multiple testing [130].

***Aim 1: To characterize the effects of switching to VLNCCs plus ECIG-Hi or ECIG-Lo nicotine doses on abuse liability among daily and intermittent smokers.*** Our primary measures of abuse liability will be CPD (product use) and nicotine equivalent (TNE) levels (nicotine compensation). We hypothesize that compared with the VLNC+ECIG-Lo phase, smokers will show decreased CPD and TNE levels during the VLNC+ECIG-Hi phase. To address these hypotheses, we will use GLMM to evaluate the effects of ECIG dose on measures of nicotine abuse liability, including cigarettes per day and TNE levels.

***Aim 2 (Exploratory): To explore the effects of switching to VLNCCs plus ECIG-Hi or ECIG-Lo nicotine doses on abuse liability using biochemical measures of product use, compensation, and toxicant exposure, and self-reported measures of withdrawal, craving, affect, and satisfaction.*** On an exploratory basis, we will examine the differences of ECIG dose (VLNC+ECIG-Lo vs. VLNC+ECIG-Hi) on additional measures of abuse liability, including ECIG puff count, withdrawal, craving, negative affect, minor tobacco alkaloid (MA) levels, acrolein DNA adduct levels, expired CO, RRE (i.e., purchase tasks), and liking (implicit attitudes, perceived harm, product satisfaction ratings). To address this exploratory aim, we will first use GLMM to evaluate the effects of ECIG dose on the retrospective questionnaire (weekly MNWS, PANAS, QSU) and daily diary (i.e., ecological momentary assessment [EMA]) measures of ECIG puff counts, withdrawal craving affect and satisfaction. To analyze the EMA data of these same constructs, we will use generalized time-varying effect modeling (TVEM)

[131, 132], using the TVEM SAS Macro [133], to evaluate the functional form of these measures of abuse liability over time between high and low ECIG conditions and between ITS and DS groups. These models fit a generalized mixed model with a spline function for characterizing changing abuse liability for the within-subjects conditions (using randomized counterbalancing to address order effects) [134, 135]. Moreover, GLMM will evaluate volatility, as defined by defined by Cofta-Woerpel and colleagues [88], as a function of ECIG dose. Conservatively assuming 15% attrition, 75% compliance and a minimum of five daily EMA measures, each 3-week ECIG dose period should provide n= 5355 observations for each group of ITS and DS smokers respectively. As such, TVEM analyses of EMA-sampled data should have sufficient power for these analyses. We will also use GLMM to evaluate the effects of ECIG dose on measures of minor tobacco alkaloid (MA) levels, acrolein DNA adduct levels, expired CO levels, RRE (i.e., purchase tasks), and liking (implicit attitudes, perceived harm, product satisfaction ratings).

**Aim 3 (exploratory): To explore the effects of switching from usual-brand cigarettes to VLNCCs, and from VLNCCs to VLNCC+ECIGs on measures of abuse liability.** On an exploratory basis, we will examine potential changes in the abuse liability measures from Aims 1 & 2 between the UB cigarette and VLNCC only phases, and between those phases and the dual-use phases (VLNC+ECIG-Lo and VLNC+ECIG-Hi). We will use GLMM to evaluate the study phase (UB cigarettes, VLNCCs, VLNC+ECIG-Lo, VLNC+ECIG-Hi) and the measures of abuse liability from Aims 1 & 2 to characterize the impact of transitioning between study nicotine products over time.

**Aim 4 (exploratory): To characterize the effects of dual use of VLNCC and JUUL ECIGs on abuse liability.** On an exploratory basis, we will examine the differences in measures of abuse liability between the two phases of dual-use (VLNC+JUUL-Lo vs. VLNC+JUUL-Hi) among participants assigned to the JUUL ECIG arm. We will use GLMM to evaluate the effects of JUUL dose on measures of nicotine abuse liability, including patterns of product use (UB and VLNCC CPD, ECIG puff count), nicotine compensation (TNE, MA, expired CO), product liking (IAT, Product Evaluation Scales, perceived harm, PHR), RRE (Purchase Task indices).

**Power analysis.** Sample size determination for the current proposal focuses on our primary outcomes for the Aim 1 hypothesis. Effect size estimates are based on our U54 data using the usual brand baseline and 0.03 mg VLNCC conditions to estimate CPD and TNE from those two conditions, respectively [9]. There is no extant data to draw upon for VLNCC+ECIG-Hi or ECIG-Lo conditions for either DS or ITS. Hence, we attempted to estimate the means and standard deviations for CPD and TNE for these two conditions using data from the U54, using

**Table 1.** Anticipated effects for DS and ITS, by Phase and E-Cig group.

Primary Outcome	Phase 1: Usual Brand	Phase 2: VLNC Only	Phase 3: VLNC + ECIGs-HI	Phase 4: VLNC + ECIGs-LO
DS				
CPD	19.62 (10.18)	14.19 (10.09) a	12.80 (10.00) b	12.80 (10.00) b
TNE	63.01 (55.87)	33.54 (34.84)	59.50 (53.88)	33.08 (31.27)
log(TNE)	3.89 (0.99)	2.69 (1.65) a	3.60 (1.28) c	2.72 (1.62) b
ITS				
CPD	3.42 (3.44)	2.47 (3.44) a	1.57 (3.44) c	1.57 (3.44) c
TNE	32.5 (17.53)	10 (9.36)	28.37 (22.24)	15.88 (11.16)
log(TNE)	3.31 (0.67)	1.74 (1.49) a	3.07 (0.80) c	2.31 (1.29) c

Primary outcomes are for nicotine compensation (TNE) and CPD. **a**-Significant change between Phase 1 & 2 expected; **b**-No significant change from Phase 2 to 3 expected; **c**-Significant change from Phase 2 to 3 expected.

the entire sample for DS, and for ITS, limiting the sample to participants in the lowest centile of baseline CPD (<7.3 cigarettes per day). These presumptive means and standard deviations are provided in **Table 1**. While these estimates are not exact they provide a reasonable estimate of the behavior of two groups that vary significantly in their CPD

**Table 2.** Power Estimates.

Contrast	Anticipated Effect Sizes		Power		Minimum Detectable Effect Size	
	DS	CPD (R.R.*)	Log(TNE) ( $d_z^{**}$ )	CPD	Log(TNE)	CPD R.R. (Power)
Within Group						
Brand v. VLNC	0.72	-0.78	$\geq 99\%$	$\geq 99\%$	0.89 (83%)	-0.39 (82%)
VLNC v. VLNC-ECIG-HI	0.90	0.56	61.4% x	$\geq 99\%$	0.88 (82%)	0.35 (81%)
VLNC v. VLNC-ECIG-LO	0.90	0.02	61.4% x	5% x	0.88 (82%)	0.36 (82%)
VLNC-ECIG-HI v. VLNC-ECIG-LO	1.00	-0.55	5% x	$\geq 99\%$	1.13 (81%)	-0.35 (80%)
ITS						
Brand v. VLNC	0.72	-1.15	93.9%	$\geq 99\%$	0.76 (82%)	-0.35 (81%)
VLNC v. VLNC-ECIG-HI	0.64	0.96	98.7%	$\geq 99\%$	0.73 (80%)	0.35 (83%)
VLNC v. VLNC-ECIG-LO	0.64	0.37	98.7%	85.7%	0.73 (80%)	0.35 (80%)
VLNC-ECIG-HI v. VLNC-ECIG-LO	1.00	-0.63	5% x	$\geq 99\%$	1.40 (82%)	-0.35 (82%)

\*Risk Ratio. \*\* Standardized effect size accounting for correlation. xNo change expected.

rate across visits ranged from 92%-100%), we based our power analysis on n = 67 DS and n = 67 ITS.

**Table 2** provides power estimates for respective contrasts. For within-group effects the overall posited correlation between adjacent phases was 0.4. Each power estimate was derived from K = 1000 Monte Carlo simulations. **Table 2** summarizes minimally detectable effects, given the anticipated sample size, alpha = 0.05, and the correlations due to repeated measures.

**Table 2** also includes minimum detectable effects and corresponding power for each contrast. Minimum detectable effects for CPD (i.e., 80-83% Power) range for Risk Ratios indicating 11% to 40% relative changes for within-group contrasts. Absolute values for standardized effect sizes that constitute minimum detectable effects for log(TNE) (i.e., 80% Power) range from absolute values of  $d_z$  = 0.35 to 0.39 for within-group contrasts. While we do not anticipate significant changes in CPD from Phases 2 to Phase 3 or 4 among DS participants, the study will be powered to detect a risk ratio for CPD of 0.88 for VLNC vs. ECIG-HI or ECIG-LO, and a risk ratio of 1.13 for the difference in CPD between VLNC + ECIG-HI and VLNC + ECIG-LO. Similarly, among DS participants we do not anticipate a change in log(TNE) moving from VLNC to VLNC-ECIG-LO, however the sample will provide power to detect a standardized effect size of  $d_z \geq 0.36$ . Among ITS participants, we do not anticipate differences between VLNC + ECIG-HI and VLNC + ECIG-LO in CPD but the sample will provide power to detect a risk ratio of 1.40 if an effect does occur. Power estimates for the exploratory Aims 2, 3, and 4 analyses focuses on the GLMMs for self-report and volatility measures; TVEM approaches will have many more observations than either of these, however fitting the functional form of change over time, and therefore its final parameterization will be largely data-dependent. Assuming alpha = 0.05 and a correlation of r = 0.5 for repeated measures, a sample of n = 67 DS participants provides 80% power for the GLMM to detect a Cohen's f = 0.17. The Aim 4 hypotheses are considered exploratory and were not subject to power analyses, but we should have adequate statistical power to detect the hypothesized differences because it will use the same sample size, design, and outcome measures as Aims 1 & 2.

and variation in their behavior when exposed to conditions of relatively more (Usual Brand) vs. less (0.03 mg) nicotine availability. Power estimates are based on Monte Carlo simulation or calculations using G\*Power 3.0 [136]. We anticipate enrollment of up to 380 participants (including at least 80 ITS). Assuming 15% loss to attrition (in our U54 the completion

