participant is experiencing sooner rather than the next scheduled contact, which is approximately 21 days after the visit. Participants are asked to bring all VLNCC products back at each visit whether opened or unopened for purposes of accounting (see Appendix KK).

The VLNCCs are made from genetically engineered tobacco strains that vary in nicotine content and are produced by RTI International (Research Triangle Park, NC), under NIDA contract (NOT-DA-14-004). As noted earlier, the VLNCC dosage, 0.03 mg, was selected from a multisite FDA-sponsored TCORS (U54DA031659 Project 1; PIs: [name] & [name]) designed to identify a dosage that was minimally reinforcing yet acceptable to smokers.

**COVID-19 adaptation:** Participants will be mailed their 3-week allotment of VLNCCs prior to the start of this phase.

**Phases 3 & 4: VLNCC+ECIG (weeks 5-7, 8-10).** During Phases 3 & 4, participants will be provided with the same weekly allocation of VLNCCs as in phase 2, as well as a supply of e-cigs. During these phases, participants will be encouraged to freely use any combination of the VLNCCs and their assigned ECIG product, ECIG-Hi or ECIG-Lo, randomized within-subjects by phase (i.e., Phase 3: ECIG-Hi, Phase 4: ECIG-Lo; or Phase 3: ECIG-Lo, Phase 4: ECIG-Hi). Those assigned to the eGo ECIG arm will receive 2 eGo LCD batteries (1100 mA; 3.3V battery) with puff counter and charge level display, 1 e-cig Universal AC-USB Adapter, 1 USB recharger, a 3 week supply (21 days) of 510 XL Dual Coil Cartomizers (1.5 Ω), a user manual, and a carrying pouch at the beginning of phases 3 and 4. The ECIG-Hi and ECIG-Lo cartomizers will contain 1 ml of 36 mg/ml or 8 mg/ml nicotine solution, respectively, in the flavor (tobacco, fruit, cream, or menthol) of each participant's choice.

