## Measures

**In-person assessment of product use, smoking behavior, and withdrawal.** At each in-person or virtual session, participants will provide a urine sample to measure TNE and MA, and provide expired CO (except at screening, where urine for TNE/MA is not collected because participants are not on study product yet). If the session is conducted virtually, expired CO will not be collected. Research assistants will also complete a Time Line Follow Back (TLFB [99]) interview to record nicotine product use up to 30 days before screening and/or up to and including last contact, including CPD (VLNCC and own brand) and number of e-cig sessions per day. The *primary* measure of CPD will come from the daily diary data. TLFB will be used as a secondary source to supplement missing data. Participants will be required to return used and unused VLNCC packs and e-cig cartomizers at each session for compliance/accounting analysis. Cartomizer weight, before distribution and upon return will provide an estimate of total product use, which will be used in conjunction with the diary data. Participants will also complete a computerized battery of questionnaires, including nicotine withdrawal (Minnesota Nicotine Withdrawal Scale; MNWS [100]), craving (Questionnaire of Smoking Urges-Brief; QSU-Brief [101]) and affect (Positive and Negative Affect Scales; PANAS [102]). Unlike the diary data which is obtained daily, or the EMA assessments that occur in real-time, these questionnaire measures cover broader segments of time (i.e., past 7 days). Missing assessments or items are expected and acceptable and are not considered a protocol deviation/violation.

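### The primary CPD test of ECIG-Hi against ECIG-Lo has no fixed unit, covariance structure or standard-error method, and plain Poisson (or scaled daily Poisson) would have a badly inflated false-positive rate on Table 1's own figures.

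*Combined protocol and SAP*

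**What the plan says.** The General Data Analytic Approach (section D, Statistical Approach & Expected Outcomes) opens: "We will conduct repeated measures analyses (i.e., across time) using generalized linear mixed modeling". It then gives the rule by data type: "Continuous and count data will be analyzed using linear and Poisson regression, respectively". Poisson is the only count distribution named. For Aim 1 it says "we will use GLMM to evaluate the effects of ECIG dose on measures of nicotine abuse liability, including cigarettes per day", and TNE is the other primary outcome. Under Measures, the primary "measure of CPD will come from the daily diary data", so the raw data are one count per day over a three-week phase.

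On departures from assumptions, the plan will inspect residual plots, use formal tests where possible, and then: "we will address violations of assumptions using transformations, robust estimators, stratification, and/or scaling coefficients". The example given is the log form for TNE. Nothing specific is said for CPD.

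Table 1 gives anticipated CPD as mean (SD), identical under Hi and Lo: 12.80 (10.00) for daily smokers (DS) and 1.57 (3.44) for intermittent smokers (ITS). For the within-group power calculations, "the overall posited correlation between adjacent phases was 0.4".

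**The concern.** A Poisson model takes its standard error from the mean. Table 1 implies variances many times the mean, and a correlation of 0.4 between phases means that much of this spread is a person smoking more in one phase than in another for reasons unrelated to dose. A subject intercept removes stable differences between people but not this subject-by-phase variation. Nor does it average out over diary days, because all days in one phase share it. A model that treats the days as independent given the person therefore gains precision it does not have.

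At stake is one of two primary outcomes. A chance difference in CPD could be reported as an effect of e-cigarette nicotine concentration, in a study meant to inform FDA regulation. The planned False Discovery Rate correction cannot repair this, because it takes the p-values as given.

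**Working it through.** **Inputs.** Means and SDs from Table 1; r = 0.4 and n = 67 per group from the power analysis; 21 days per dose phase (weeks 5–7 and 8–10). Assumptions: two-sided 5% test; Table 1's SD is the between-person SD of phase CPD; r = 0.4 applies to CPD.

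**1. The plan's own power figures.** Take one Poisson count per person per phase and the ordinary Poisson SE for the log rate ratio, √[(1/m₁ + 1/m₂)/67]. For DS VLNC against Hi this is √[(1/14.19 + 1/12.80)/67] = 0.047, against |ln(12.80/14.19)| = 0.103. Simulating such counts with correlation 0.4 gives:

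| Contrast | Table 2 | Reproduced |
|---|---|---|
| DS, VLNC v Hi | 61.4% | 61% |
| ITS, usual brand v VLNC | 93.9% | 94% |
| ITS, VLNC v Hi | 98.7% | 98% |
| DS, Hi v Lo at ratio 1.13 | 81% | 78–80% |
| ITS, Hi v Lo at ratio 1.40 | 82% | 80–81% |

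Table 2 is thus consistent with Poisson variance at one count per phase. With Table 1's SDs and r = 0.4, the first row would be about 18%, so those SDs do not appear to have been used for CPD power.

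**2. Overdispersion in Table 1.** Variance over mean is 10.00²/12.80 = 7.8 (DS) and 3.44²/1.57 = 7.5 (ITS). As SD ratios these are 2.80 and 2.75, but they are total ratios. Stable differences between people cancel in a within-person contrast, so the relevant factor is smaller by √(1 − 0.4): 2.80 × 0.775 = 2.17 (DS) and 2.75 × 0.775 = 2.13 (ITS).

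**3. False-positive rate under no dose effect.** The true variance of a person's Hi–Lo difference is 2·SD²(1 − r). Poisson assumes 2·mean/d, where d is the number of counts per phase. The SE is therefore too small by R = SD√(1 − r)/√(mean/d), and the rejection rate is 2[1 − Φ(1.96/R)]. This does not depend on n. In a balanced design, a subject intercept leaves the dose estimate and its Poisson SE unchanged.

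- One count per phase, r = 0.4: R = 2.17 and 2.13, giving 36.5% (DS) and 35.7% (ITS).
- One count per phase, higher r, DS: R = 10√0.3/√12.8 = 1.53 at r = 0.7 gives 20%; R = 1.08 at r = 0.85 gives 7%; R = 0.88 at r = 0.9 gives about 3%.
- 21 daily counts, r = 0.4: R = 2.17 × √21 = 9.9 (DS) and 2.13 × √21 = 9.8 (ITS), giving 84% in both groups. At r = 0.9 it is still about 62–63%.

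**4. Simulation** (gamma person and person-by-phase means matched to Table 1, Poisson days, n = 67, no dose effect, r = 0.4):

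| Analysis | DS | ITS |
|---|---|---|
| One count per phase, unscaled | 36% | 36% |
| 21 daily counts, unscaled | 84% | 84% |
| 21 daily counts, Pearson scale, no subject effects | 56% | 57% |
| 21 daily counts, Pearson scale after subject effects | 74–75% | 78–79% |
| 21 daily counts, robust variance clustered on subject | 6% | 7% |

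With 16 completed days (75% completion, the rate given for EMA and assumed here for the diary), the unscaled daily rate is 82–83%. Scaling fails on daily counts because it measures spread between days and does not capture the correlation of days within a person's phase.

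**The case against.** A reader might infer that the primary test is Poisson on daily counts, with SDs 2.8 times Poisson, so that a null dose effect would be declared significant in most trials. The documents do not support that:

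- The plan names the diary as the data source, not the day as the unit. It does not limit the mixed model to a random intercept or commit to model-based standard errors.
- Table 2 matches one count per phase. If that is the intended unit, the unscaled rate is about 36% at r = 0.4, and near nominal by r = 0.85–0.9.
- The 2.8 is a total ratio; about 2.15 governs this contrast at r = 0.4.
- Variances this far above the mean should fail the promised residual checks and trigger the remedy clause. That clause lists robust estimators, which restore about 5–7% if clustered on subject. At one count per phase, a Pearson scale from a model without subject effects gives 1.6%, which is conservative.
- The plan itself calls Table 1's values inexact, and the ITS SD of 3.44 is carried unchanged through all four phases while the mean falls. At the ITS baseline, variance over mean is 3.44²/3.42 = 3.5.

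All of this stands and limits the point. What it does not do is settle the analysis. The same clause also lists scaling coefficients, which leave gross error on daily counts, and the choice is left until after the data are inspected.

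**Conclusion.** The point holds as one about an unfixed primary analysis, not as a demonstrated error rate for this trial. On the plan's own mean, SD and correlation, the false-positive rate for Hi against Lo runs from about 5–7% (subject-clustered robust variance), through about 35–37% (one unscaled count per phase) and 57–78% (scaled daily counts), to about 84% (unscaled daily counts). Which of these applies depends on a choice the plan does not make.

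The figures rest on reading Table 1's SD as a between-person SD of phase CPD. If it is a single-day SD, the unscaled daily rate lies between about 36% and 82%, depending on how much of the variation is person-by-phase. They also rest on r = 0.4: at r = 0.7, one unscaled count per phase gives about 18–20%. This should be fixed before analysis. It does not invalidate the design.

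**What to change.** State the primary CPD analysis in the SAP as one of two forms:

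- (a) daily counts by Poisson or negative binomial regression, with a subject intercept, a random subject-by-phase effect, and sandwich variance clustered on subject; or
- (b) one mean CPD per participant per phase, compared within person. In simulation this kept the error at about 3–5%.

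Rule out unscaled Poisson for CPD and scale-only correction of daily counts, and apply the same rule to e-cigarette puff counts. No new data or procedures are needed. The cost is SAP wording and wider confidence intervals that reflect the variation Table 1 already anticipates.

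### The Aim 1 model for the randomised dose-order crossover does not specify a period term, so a Phase 3 to Phase 4 trend would cost precision and, if dropout differs by order, cause a small bias

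*Combined protocol and SAP*

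**What the plan says.** The Procedures section sets up a two-period, two-order crossover. The dose is "randomized within-subjects by phase (i.e., Phase 3: ECIG-Hi, Phase 4: ECIG-Lo; or Phase 3: ECIG-Lo, Phase 4: ECIG-Hi", and the two periods follow directly on each other: "Phases 3 & 4: VLNCC+ECIG (weeks 5-7, 8-10".

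The Aim 1 hypothesis, under Statistical Approach & Expected Outcomes, is that "compared with the VLNC+ECIG-Lo phase, smokers will show decreased CPD and TNE levels during the VLNC+ECIG-Hi phase". Its analysis is one sentence: "we will use GLMM to evaluate the effects of ECIG dose on measures of nicotine abuse liability", with CPD and TNE given as the outcomes. The only wording about time that governs it is the general statement "We will conduct repeated measures analyses (i.e., across time) using generalized linear mixed modeling".

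The analysis text mentions order once, for the exploratory time-varying effect models of Aim 2, and relies there on the design: "using randomized counterbalancing to address order effects". Aim 3 does have a phase factor, "We will use GLMM to evaluate the study phase (UB cigarettes, VLNCCs, VLNC+ECIG-Lo, VLNC+ECIG-Hi", but its levels are products and doses, so it does not distinguish Phase 3 from Phase 4.

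**The concern.** A trend between the two dual-use phases is plausible. Participants are not regular e-cigarette users (Study overview) and are first trained on the device at the start of Phase 3 (Procedures). Under Duration of product exposure, the protocol says that it has no data on how long e-cigarette use takes to settle.

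If such a trend exists, it moves the high-minus-low difference down in one order group and up in the other. With equal groups the average is right. The spread between the groups is still counted as noise, however, so the standard error is too large and the test is conservative. If the groups also lose people unequally after Phase 3, the trend no longer cancels and part of it passes into the dose estimate. Both effects can be avoided with data that the trial already collects.

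**Working it through.** **Inputs**
- Analysed n: 67 per smoker group (Power analysis). I use 68, so that the orders can be equal at 34 each; 80 × 0.85 = 68.
- Alpha 0.05 (Power analysis), taken as two-sided because sidedness is not stated.
- Correlation between adjacent phases: 0.4 (Power analysis).
- log(TNE), daily smokers: 3.60 (SD 1.28) on high dose and 2.72 (SD 1.62) on low dose (Table 1).
- dz for high v low in daily smokers: 0.35 minimum detectable, 0.55 anticipated (Table 2, absolute values).
- Phase 3 to Phase 4 trend π: not given. Assumed 0 to 1 SD of the outcome, with SD 1 in both phases.

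**Step 1: reproduce the plan's figure.** SD of the difference = √(1.28² + 1.62² − 2 × 0.4 × 1.28 × 1.62) = 1.614, and dz = 0.88/1.614 = 0.545 (stated 0.55). A two-sided paired t-test with n = 67 has power 80.6% at dz 0.35 (stated 80%) and 99.3% at dz 0.55 (stated at least 99%). The plan's figures reproduce with no trend between the phases.

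**Step 2: add a trend, equal orders.** The variance of a within-person difference is 2(1 − 0.4) = 1.2. Its mean is δ − π for high-first and δ + π for low-first, so with 34 in each the average is δ and there is no bias. The true variance of that average is 1.2/n, but a dose-only analysis estimates (1.2 + π²)/n. The critical value is in effect raised from 1.996 to 1.996 × √(1 + π²/1.2), so

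power ≈ Φ(dz√n − 1.996 × √(1 + π²/1.2)).

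For π = 0.5: 1 + 0.25/1.2 = 1.208; 1.996 × √1.208 = 2.194; 0.35 × √68 = 2.886; Φ(2.886 − 2.194) = Φ(0.692) = 76%.

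| Trend π (SD) | 1 + π²/1.2 | Effective critical value | Dose-only power, dz 0.35 | With period term |
|---|---|---|---|---|
| 0 | 1.000 | 1.996 | 81% | 81% |
| 0.25 | 1.052 | 2.047 | 80% | 81% |
| 0.5 | 1.208 | 2.194 | 76% | 81% |
| 0.75 | 1.469 | 2.419 | 68% | 81% |
| 1 | 1.833 | 2.703 | 57% | 81% |

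Simulation of the balanced design agrees to within a percentage point. With a period term π drops out, at the cost of one degree of freedom. With no dose effect and π = 0.5, the formula gives a dose-only rejection rate of 2Φ(−2.194) = 2.8%; simulation gives about 3%.

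At the anticipated effect, 0.55 × √68 = 4.535 and Φ(4.535 − 2.194) = 99% for π = 0.5.

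**Step 3: unequal dropout after Phase 3.** Among completers the bias is π × (n₁ − n₂)/(n₁ + n₂). With 40 per order and losses of 5% v 25%, 38 and 30 remain, so the bias is 8/68 = 11.8% of the trend. A mixed model on all available data was simulated with 80 randomised equally, 1,500 runs per scenario, and a trend of 0.5 SD of the within-person difference. In SDs of that difference:
- 15% v 15% dropout: bias about zero.
- 5% v 25%: about 0.03.
- 10% v 36%: about 0.05.

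With a period term the bias is about zero in all three. The null rejection rate of the dose-only model was not inflated in any (3.1%, 3.5% and 3.9%). The sign of the bias depends on the direction of the trend and on which order loses more people.

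**The case against.** The Aim 1 sentence names the effect of interest and is not a model formula. It does not list random effects or a covariance structure either, and the general reference to repeated measures over time could be read to allow a time term. That stands: the plan leaves period unspecified, and a reader should not infer that it rules period out.

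The protocol also reports little change in VLNCC cigarettes per day beyond week 3, and Phase 3 begins after three VLNCC weeks. That makes a large trend in cigarette count less likely, but it says nothing about e-cigarette uptake.

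Several stronger readings are tempting, and the documents do not support them.
- **Table 1 as a guide to the trend.** Daily-smoker CPD falls from 19.62 to 14.19 between Phases 1 and 2, roughly half an SD. That is the assumed effect of changing product, not drift over time, so it cannot set the size of a Phase 3 to Phase 4 trend.
- **77% retention as evidence of bias.** That figure runs to the end of the study, and randomisation is at Visit 1. It can therefore include losses before Phase 3, which contribute no dual-use data, and it is not split by order. Equal losses in both orders give no bias.
- **The primary contrast as underpowered or prone to false positives.** For log(TNE) at the anticipated effect power is barely touched, and the dose-only test errs on the conservative side.

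The planned missing-data tests, pattern-mixture models and sensitivity analyses are useful, but they do not themselves adjust for period.

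**Conclusion.** The concern holds in limited form. The Aim 1 GLMM should name period, because counterbalancing does not remove a trend from the error term. The main harm is lost precision for effects near the detection limit: at dz 0.35, power is about 80% under a 0.25 SD trend, 76% under 0.5 SD and 57% under 1 SD, against about 81% with a period term. Bias is secondary, conditional on unequal dropout by order, and small.

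These sizes rest on assumed trends, equal unit SDs, correlation 0.4, equal orders and assumed dropout splits. The documents supply only the correlation. The calculation is on a normal scale and speaks to log(TNE); it does not quantify the loss for CPD, which the plan treats as a count. CPD is nevertheless where a modest effect is most likely, since Table 2 anticipates a high v low risk ratio of 1.00.

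**What to change.** In the Aim 1 paragraph of Statistical Approach & Expected Outcomes, specify the GLMM with fixed effects for dose (high v low) and period (Phase 3 v Phase 4) and a random participant effect. Use the same period term for the Aim 2 and Aim 4 dose contrasts. A sequence term is optional: the gain shown here comes from period alone.

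The cost is one sentence of analysis text and one degree of freedom. No new data are needed, and almost nothing is lost if there is no trend. Stating the term in advance also keeps the choice of model independent of the results.
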